### Schedule of Pharmacokinetic and Immunogenicity Samples

Visit	Timepoint	Sample Type(s)
Day 1 of Cycle 1 (Cohorts 1–6 only)	Prior to atezolizumab infusion	Atezolizumab PK and ADA (serum)
	30 ( $\pm$ 10) minutes following end of atezolizumab infusion	Atezolizumab PK (serum)
Day 15 of Cycle 1 (Cohort 7 only)	Prior to atezolizumab infusion	Atezolizumab PK and ADA (serum)
	30 ( $\pm$ 10) minutes following end of atezolizumab infusion	Atezolizumab PK (serum)
Day 1 of Cycles 2, 4, 8, 12, and 16	Prior to atezolizumab infusion	Atezolizumab PK and ADA (serum)
Day 15 of Cycle 3	Prior to atezolizumab infusion	Atezolizumab PK and ADA (serum)
	Prior to cobimetinib dose	Cobimetinib PK (plasma)
	30 ( $\pm$ 10) minutes following end of atezolizumab infusion	Atezolizumab PK and ADA (serum)
	2–4 hours after cobimetinib dose	Cobimetinib PK (plasma)
Atezolizumab treatment discontinuation visit	At visit	Atezolizumab PK and ADA (serum)
> 90 days after last atezolizumab infusion	At visit	Atezolizumab PK and ADA (serum)

ADA= anti-drug antibody; NA= not applicable; PK= pharmacokinetic.

Notes: Except for Day 1 of Cycle 1 all other study visits and assessments during the treatment period should be performed within  $\pm$ 3 days of the scheduled date.

Study assessments may be delayed or moved ahead of the window to accommodate holidays, vacations, and unforeseen delays.

## **Appendix 3**

### **Response Evaluation Criteria in Solid Tumors, Version 1.1 (RECIST v1.1)**

Selected sections from the Response Evaluation Criteria in Solid Tumors, Version 1.1 (RECIST v1.1) (Eisenhauer et al. 2009), are presented below, with slight modifications from the original publication and the addition of explanatory text as needed for clarity.

#### **TUMOR MEASURABILITY**

At baseline, tumor lesions/lymph nodes will be categorized as measurable or non-measurable as described below. All measurable and non-measurable lesions should be assessed at screening and at subsequent protocol-specified tumor assessment timepoints. Additional assessments may be performed as clinically indicated for suspicion of progression.

#### **DEFINITION OF MEASURABLE LESIONS**

##### **Tumor Lesions**

Tumor lesions must be accurately measured in at least one dimension (longest diameter in the plane of measurement is to be recorded) with a minimum size as follows:

- 10 mm by computed tomography (CT) or magnetic resonance imaging (MRI) scan (CT/MRI scan slice thickness/interval  $\leq$  5 mm)
- 10-mm caliper measurement by clinical examination (lesions that cannot be accurately measured with calipers should be recorded as non-measurable)
- 20 mm by chest X-ray

##### **Malignant Lymph Nodes**

To be considered pathologically enlarged and measurable, a lymph node must be  $\geq$  15 mm in the short axis when assessed by CT scan (CT scan slice thickness recommended to be  $\leq$  5 mm). At baseline and follow-up, only the short axis will be measured and followed. Additional information on lymph node measurement is provided below (see "Identification of Target and Non-Target Lesions" and "Calculation of Sum of Diameters").

---

 For clarity and for consistency within this document, the section numbers and cross-references to other sections within the article have been deleted and minor changes have been made.

## **Appendix 3**

### **Response Evaluation Criteria in Solid Tumors, Version 1.1 (RECIST v1.1) (cont.)**

#### **DEFINITION OF NON-MEASURABLE LESIONS**

Non-measurable tumor lesions encompass small lesions (longest diameter < 10 mm or pathological lymph nodes with short axis  $\geq$  10 mm but < 15 mm) as well as truly non-measurable lesions. Lesions considered truly non-measurable include leptomeningeal disease, ascites, pleural or pericardial effusion, inflammatory breast disease, lymphangitic involvement of skin or lung, peritoneal spread, and abdominal mass/abdominal organomegaly identified by physical examination that is not measurable by reproducible imaging techniques.

#### **SPECIAL CONSIDERATIONS REGARDING LESION MEASURABILITY**

Bone lesions, cystic lesions, and lesions previously treated with local therapy require particular comment, as outlined below.

##### **Bone Lesions:**

- Technetium-99m bone scans, sodium fluoride positron emission tomography scans, and plain films are not considered adequate imaging techniques for measuring bone lesions. However, these techniques can be used to confirm the presence or disappearance of bone lesions.
- Lytic bone lesions or mixed lytic-blastic lesions with identifiable soft tissue components that can be evaluated by cross-sectional imaging techniques such as CT or MRI can be considered measurable lesions if the soft tissue component meets the definition of measurability described above.
- Blastic bone lesions are non-measurable.

##### **Cystic Lesions:**

- Lesions that meet the criteria for radiographically defined simple cysts should not be considered malignant lesions (neither measurable nor non-measurable) since they are, by definition, simple cysts.
- Cystic lesions thought to represent cystic metastases can be considered measurable lesions if they meet the definition of measurability described above. However, if non-cystic lesions are present in the same patient, these are preferred for selection as target lesions.

##### **Lesions with Prior Local Treatment:**

- Tumor lesions situated in a previously irradiated area or in an area subjected to other loco-regional therapy are usually not considered measurable unless there has been demonstrated progression in the lesion.

## **Appendix 3**

### **Response Evaluation Criteria in Solid Tumors, Version 1.1 (RECIST v1.1) (cont.)**

#### **METHODS FOR ASSESSING LESIONS**

All measurements should be recorded in metric notation, using calipers if clinically assessed. All baseline evaluations should be performed as close as possible to the treatment start and never more than 4 weeks before the beginning of the treatment.

The same method of assessment and the same technique should be used to characterize each identified and reported lesion at baseline and during the study. Imaging-based evaluation should always be the preferred option.

#### **CLINICAL LESIONS**

Clinical lesions will only be considered measurable when they are superficial and  $\geq 10$  mm in diameter as assessed using calipers (e.g., skin nodules). For the case of skin lesions, documentation by color photography, including a ruler to estimate the size of the lesion, is suggested.

#### **CHEST X-RAY**

Chest CT is preferred over chest X-ray, particularly when progression is an important endpoint, since CT is more sensitive than X-ray, particularly in identifying new lesions. However, lesions on chest X-ray may be considered measurable if they are clearly defined and surrounded by aerated lung.

#### **CT AND MRI SCANS**

CT is the best currently available and reproducible method to measure lesions selected for response assessment. In this guideline, the definition of measurability of lesions on CT scan is based on the assumption that CT slice thickness is  $\leq 5$  mm. When CT scans have slice thickness of  $>5$  mm, the minimum size for a measurable lesion should be twice the slice thickness. MRI is also acceptable.

If prior to enrollment it is known that a patient is unable to undergo CT scans with IV contrast because of allergy or renal insufficiency, the decision as to whether a non-contrast CT or MRI (without IV contrast) will be used to evaluate the patient at baseline and during the study should be guided by the tumor type under investigation and the anatomic location of the disease. For patients who develop contraindications to contrast after baseline contrast CT is done, the decision as to whether non-contrast CT or MRI (enhanced or non-enhanced) will be performed should also be based on the tumor type and the anatomic location of the disease, and should be optimized to allow for comparison with the prior studies if possible. Each case should be discussed with the radiologist to determine if substitution of these other approaches is possible and, if not, the patient should be considered not evaluable from that point forward. Care must be taken in measurement of target lesions and interpretation of non-target disease or new

### **Appendix 3**

## **Response Evaluation Criteria in Solid Tumors, Version 1.1 (RECIST v1.1) (cont.)**

lesions on a different modality, since the same lesion may appear to have a different size using a new modality.

### **ENDOSCOPY, LAPAROSCOPY, ULTRASOUND, TUMOR MARKERS, CYTOLOGY, HISTOLOGY**

Endoscopy, laparoscopy, ultrasound, tumor markers, cytology, and histology cannot be utilized for objective tumor evaluation.

### **ASSESSMENT OF TUMOR BURDEN**

To assess objective response or future progression, it is necessary to estimate the overall tumor burden at baseline and use this as a comparator for subsequent measurements.

### **IDENTIFICATION OF TARGET AND NON-TARGET LESIONS**

When more than one measurable lesion is present at baseline, all lesions up to a maximum of five lesions total (and a maximum of two lesions per organ) representative of all involved organs should be identified as target lesions and will be recorded and measured at baseline. This means that, for instances in which patients have only one or two organ sites involved, a maximum of two lesions (one site) and four lesions (two sites), respectively, will be recorded. Other lesions (albeit measurable) in those organs will be considered non-target lesions.

Target lesions should be selected on the basis of their size (lesions with the longest diameter) and be representative of all involved organs, but in addition should lend themselves to reproducible repeated measurements. It may be the case that, on occasion, the largest lesion does not lend itself to reproducible measurement, in which circumstance the next largest lesion that can be measured reproducibly should be selected.

Lymph nodes merit special mention since they are normal anatomical structures that may be visible by imaging even if not involved by tumor. As noted above, pathological nodes that are defined as measurable and may be identified as target lesions must meet the criterion of a short axis of  $\geq 15$  mm by CT scan. Only the short axis of these nodes will contribute to the baseline sum. The short axis of the node is the diameter normally used by radiologists to judge if a node is involved by solid tumor. Lymph node size is normally reported as two dimensions in the plane in which the image is obtained (for CT, this is almost always the axial plane; for MRI, the plane of acquisition may be axial, sagittal, or coronal). The smaller of these measures is the short axis. For example, an abdominal node that is reported as being 20 mm  $\times$  30 mm has a short axis of 20 mm and qualifies as a malignant, measurable node. In this example, 20 mm should be recorded

## **Appendix 3**

### **Response Evaluation Criteria in Solid Tumors, Version 1.1 (RECIST v1.1) (cont.)**

as the node measurement. All other pathological nodes (those with short axis  $\geq 10$  mm but  $< 15$  mm) should be considered non-target lesions. Nodes that have a short axis of  $< 10$  mm are considered non-pathological and should not be recorded or followed.

All lesions (or sites of disease) not selected as target lesions (measurable or non-measurable), including pathological lymph nodes, should be identified as non-target lesions and should also be recorded at baseline. Measurements are not required. It is possible to record multiple non-target lesions involving the same organ as a single item on the Case Report Form (CRF) (e.g., "multiple enlarged pelvic lymph nodes" or "multiple liver metastases").

#### **CALCULATION OF SUM OF DIAMETERS**

A sum of the diameters (longest diameter for non-lymph node lesions, short axis for lymph node lesions) will be calculated for all target lesions at baseline and at each subsequent tumor assessment as a measure of tumor burden.

#### **Measuring Lymph Nodes**

Lymph nodes identified as target lesions should always have the actual short axis measurement recorded (measured in the same anatomical plane as the baseline examination), even if the node regresses to  $< 10$  mm during the study. Thus, when lymph nodes are included as target lesions, the sum of diameters may not be zero even if complete response (CR) criteria are met, since a normal lymph node is defined as having a short axis of  $< 10$  mm.

#### **Measuring Lesions That Become Too Small to Measure**

During the study, all target lesions (lymph node and non-lymph node) recorded at baseline should have their actual measurements recorded at each subsequent evaluation, even when very small (e.g., 2 mm). However, sometimes lesions or lymph nodes that are recorded as target lesions at baseline become so faint on CT scan that the radiologist may not feel comfortable assigning an exact measurement and may report them as being too small to measure. When this occurs, it is important that a value be recorded on the CRF, as follows:

- If it is the opinion of the radiologist that the lesion has likely disappeared, the measurement should be recorded as 0 mm.
- If the lesion is believed to be present and is faintly seen but too small to measure, a default value of 5 mm should be assigned and "too small to measure" should be ticked. (Note: It is less likely that this rule will be used for lymph nodes since they usually have a definable size when normal and are frequently surrounded by fat such as in the retroperitoneum; however, if a lymph node is believed to be present and is faintly seen but too small to measure, a default value of 5 mm should be

## **Appendix 3**

### **Response Evaluation Criteria in Solid Tumors, Version 1.1 (RECIST v1.1) (cont.)**

assigned in this circumstance as well and "too small to measure" should also be ticked).

To reiterate, however, if the radiologist is able to provide an actual measurement, that should be recorded, even if it is <5 mm, and in that case "too small to measure" should not be ticked.

#### **Measuring Lesions That Split or Coalesce on Treatment**

When non-lymph node lesions fragment, the longest diameters of the fragmented portions should be added together to calculate the sum of diameters. Similarly, as lesions coalesce, a plane between them may be maintained that would aid in obtaining maximal diameter measurements of each individual lesion. If the lesions have truly coalesced such that they are no longer separable, the vector of the longest diameter in this instance should be the maximum longest diameter for the coalesced lesion.

#### **EVALUATION OF NON-TARGET LESIONS**

Measurements are not required for non-target lesions, except that malignant lymph node non-target lesions should be monitored for reduction to < 10 mm in short axis.

Non-target lesions should be noted at baseline and should be identified as "present" or "absent" and (in rare cases) may be noted as "indicative of progression" at subsequent evaluations. In addition, if a lymph node lesion shrinks to a non-malignant size (short axis < 10 mm), this should be captured on the eCRF as part of the assessment of non-target lesions.

#### **RESPONSE CRITERIA**

##### **CRITERIA FOR TARGET LESIONS**

Definitions of the criteria used to determine objective tumor response for target lesions are provided below:

- CR: Disappearance of all target lesions  
Any pathological lymph nodes must have reduction in short axis to < 10 mm.
- Partial response (PR): At least a 30% decrease in the sum of diameters of all target lesions, taking as reference the baseline sum of diameters, in the absence of CR
- Progressive disease (PD): At least a 20% increase in the sum of diameters of target lesions, taking as reference the smallest sum of diameters on study (including baseline)

In addition to the relative increase of 20%, the sum of diameters must also demonstrate an absolute increase of  $\geq 5$  mm.

## **Appendix 3**

### **Response Evaluation Criteria in Solid Tumors, Version 1.1 (RECIST v1.1) (cont.)**

- Stable disease (SD): Neither sufficient shrinkage to qualify for CR or PR nor sufficient increase to qualify for PD

#### **CRITERIA FOR NON-TARGET LESIONS**

Definitions of the criteria used to determine the tumor response for the group of non-target lesions are provided below. While some non-target lesions may actually be measurable, they need not be measured and instead should be assessed only qualitatively at the timepoints specified in the schedule of activities.

- CR: Disappearance of all non-target lesions and (if applicable) normalization of tumor marker level

All lymph nodes must be non-pathological in size (< 10 mm short axis).

- Non-CR/Non-PD: Persistence of one or more non-target lesions and/or (if applicable) maintenance of tumor marker level above the normal limits
- PD: Unequivocal progression of existing non-target lesions

#### **SPECIAL NOTES ON ASSESSMENT OF PROGRESSION OF NON-TARGET LESIONS**

##### **Patients with Measurable and Non-Measurable Disease**

For patients with both measurable and non-measurable disease to achieve unequivocal progression on the basis of the non-target lesions, there must be an overall level of substantial worsening in non-target lesions in a magnitude that, even in the presence of SD or PR in target lesions, the overall tumor burden has increased sufficiently to merit discontinuation of therapy. A modest increase in the size of one or more non-target lesions is usually not sufficient to qualify for unequivocal progression status. The designation of overall progression solely on the basis of change in non-target lesions in the face of SD or PR in target lesions will therefore be extremely rare.

##### **Patients with Non-Measurable Disease Only**

For patients with non-measurable disease only, the same general concepts apply as noted above. However, in this instance there is no measurable disease assessment to factor into the interpretation of an increase in non-measurable disease burden. Because worsening in non-measurable disease cannot be easily quantified (by definition, if all lesions are truly non-measurable), a useful test that can be applied when assessing patients for unequivocal progression is to consider if the increase in overall disease burden based on the change in non-measurable disease is comparable in magnitude to the increase that would be required to declare PD for measurable disease, that is, an increase in tumor burden representing an additional 73% increase in volume (which is equivalent to a 20% increase in diameter in a measurable lesion). Examples include an increase in a pleural effusion from "trace" to "large" or an increase in lymphangitic disease from localized to widespread. If unequivocal progression is seen, the patient

### **Appendix 3**

## **Response Evaluation Criteria in Solid Tumors, Version 1.1 (RECIST v1.1) (cont.)**

should be considered to have had overall PD at that point. While it would be ideal to have objective criteria to apply to non-measurable disease, the very nature of that disease makes it impossible to do so; therefore, the increase must be substantial.

### **NEW LESIONS**

The appearance of new malignant lesions denotes disease progression; therefore, some comments on detection of new lesions are important. There are no specific criteria for the identification of new radiographic lesions; however, the finding of a new lesion should be unequivocal, that is, not attributable to differences in scanning technique, change in imaging modality, or findings thought to represent something other than tumor (for example, some "new" bone lesions may be simply healing or flare of preexisting lesions). This is particularly important when the patient's baseline lesions show PR or CR. For example, necrosis of a liver lesion may be reported on a CT scan report as a "new" cystic lesion, which it is not.

A lesion identified during the study in an anatomical location that was not scanned at baseline is considered a new lesion and will indicate disease progression.

If a new lesion is equivocal, for example because of its small size, continued therapy and follow-up evaluation will clarify if it represents truly new disease. If repeat scans confirm there is definitely a new lesion, progression should be declared using the date of the initial scan.

### **CRITERIA FOR OVERALL RESPONSE AT A SINGLE TIMEPOINT**

[Table 1](#) provides a summary of the overall response status calculation at each response assessment timepoint for patients who have measurable disease at baseline.

### Appendix 3 Response Evaluation Criteria in Solid Tumors, Version 1.1 (RECIST v1.1) (cont.)

**Table 1 Criteria for Overall Response at a Single Timepoint: Patients with Non-Target Lesions Only**

Non-Target Lesions	New Lesions	Overall Response
CR	No	CR
Non-CR/non-PD	No	Non-CR/non-PD a
Not all evaluated	No	NE
Unequivocal PD	Yes or no	PD
Any	Yes	PD

CR=complete response; NE=not evaluable; PD=progressive disease.

a "Non-CR/non-PD" is preferred over "stable disease" for non-target disease since stable disease is increasingly used as an endpoint for assessment of efficacy in some trials; thus, assigning "stable disease" when no lesions can be measured is not advised.

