#### **SPECIAL NOTES ON RESPONSE ASSESSMENT**

Patients with a global deterioration in health status requiring discontinuation of treatment without objective evidence of disease progression at that time should be reported as "symptomatic deterioration." Every effort should be made to document objective progression even after discontinuation of treatment. Symptomatic deterioration is not a descriptor of an objective response; it is a reason for stopping study therapy. The objective response status of such patients is to be determined by evaluation of target and non-target lesions as shown in [Table 1](#).

For equivocal findings of progression (e.g., very small and uncertain new lesions; cystic changes or necrosis in existing lesions), treatment may continue until the next scheduled assessment. If at the next scheduled assessment, progression is confirmed, the date of progression should be the earlier date when progression was suspected.

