### Immune-Modified Response Evaluation Criteria in Solid Tumors (Immune-Modified RECIST) (cont.)

**Table 2 Criteria for Overall Response at a Single Timepoint: Patients with Target Lesions (with or without Non-Target Lesions)**

Target Lesions and Measurable New Lesions a	Non-Target Lesions and Non-Measurable New Lesions b	Overall Response
CR	Absent	CR
CR	Present or not all evaluated	PR
PR	Any	PR
SD	Any	SD
Not all evaluated	Any	NE
PD	Any	PD

CR = complete response; NE = not evaluable; PD = progressive disease; PR = partial response; SD = stable disease.

a Up to a maximum of five measurable new lesions total (and a maximum of two lesions per organ) can be included in the calculation of tumor burden, in addition to the target lesions identified at baseline.

b Also includes measurable new lesions in excess of five total or two per organ.

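### Appendix 3 Table 1, cited as the RECIST v1.1 overall-response rule for patients with measurable disease, is the table for patients with non-target lesions only

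*Combined protocol and SAP*

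**What the plan says.** In Appendix 3, the lead-in under Criteria for Overall Response at a Single Timepoint says that Table 1 "provides a summary of the overall response status calculation at each response assessment timepoint for patients who have measurable disease at baseline". Under Special Notes on Response Assessment, the same table is cited for patients who stop treatment with symptomatic deterioration: "The objective response status of such patients is to be determined by evaluation of target and non-target lesions as shown in" Table 1.

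The only Table 1 in Appendix 3 is headed "Criteria for Overall Response at a Single Timepoint: Patients with Non-Target Lesions Only". Its columns are non-target lesions, new lesions and overall response. Its possible results are CR, Non-CR/non-PD, NE and PD. Its footnote says that assigning stable disease "when no lesions can be measured is not advised".

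Section 4.1.1.2 requires measurable disease of every patient, and Section 4.1.3.4 repeats this for Cohort 7.

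Appendix 4 (immune-modified RECIST) uses the same lead-in sentence, but there it introduces Table 2, titled "Criteria for Overall Response at a Single Timepoint: Patients with Target Lesions (with or without Non-Target Lesions)". That table takes target lesions as an input and returns CR, PR, SD, NE or PD.

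**The concern.** Investigator-assessed RECIST v1.1 response determines the primary endpoint, ORR (Section 6.4.1), and the secondary endpoints DCR, PFS and DOR (Section 6.4.2). ORR counts CR and PR, DCR also counts SD, and PFS and DOR need the date of progression. The table that Appendix 3 names for combining lesion findings into a timepoint response has no PR, no SD and no place to enter target-lesion growth. A site that followed the citation literally would produce results that contradict the definitions printed a few pages earlier.

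A dropped table does not explain the mismatch. The printed table carries the number that both passages cite, and its title, columns, abbreviation key and footnote all belong to a non-target-only table. If a second table had been lost, the citations would still point to this one.

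**Working it through.** The plan gives no figure to reproduce. The check compares the printed table with the protocol's own definitions, one combination at a time.

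**Inputs**

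- Printed Table 1, no new lesion: the result depends on non-target status alone. CR gives CR; non-CR/non-PD gives Non-CR/non-PD; not all evaluated gives NE; unequivocal PD gives PD.
- Target-lesion definitions, Appendix 3, Criteria for Target Lesions. PR: "At least a 30% decrease in the sum of diameters of all target lesions, taking as reference the baseline sum of diameters". PD: "At least a 20% increase in the sum of diameters of target lesions, taking as reference the smallest sum of diameters on study", with an absolute increase of at least 5 mm. SD: "Neither sufficient shrinkage to qualify for CR or PR nor sufficient increase to qualify for PD".
- RECIST v1.1 column of Appendix 4 Table 1. CR needs all lesions gone. PR needs the 30% decrease without CR, new lesions or unequivocal non-target progression. PD follows from any one of target growth, unequivocal non-target progression or a new lesion.
- ORR counts CR and PR; DCR counts CR, PR and SD at 16 weeks. Non-CR/non-PD and NE are taken as none of these.

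**Enumeration**

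Four target states (CR, PR, SD, PD) times four non-target states gives 4 × 4 = 16 combinations, all without a new lesion.

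The table and the definitions agree in five: target CR with non-target CR, and each of the four target states with unequivocal non-target PD.

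They conflict in eight:

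| Target | Non-target | Printed Table 1 | Definitions | Effect at that timepoint |
|---|---|---|---|---|
| CR | Non-CR/non-PD | Non-CR/non-PD | PR | Response lost for ORR and DCR |
| PR | Non-CR/non-PD | Non-CR/non-PD | PR | Response lost for ORR and DCR |
| SD | CR | CR | SD | False response for ORR |
| SD | Non-CR/non-PD | Non-CR/non-PD | SD | Disease control lost for DCR |
| PD | CR | CR | PD | False response for ORR and DCR; progression missed |
| PD | Non-CR/non-PD | Non-CR/non-PD | PD | ORR and DCR unchanged; progression missed |
| PD | Not all evaluated | NE | PD | ORR and DCR unchanged; progression missed |
| PR | CR | CR | PR | Category only |

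The first five rows change ORR or DCR status. The next two affect only PFS and DOR. The last changes neither status nor progression: 5 + 2 + 1 = 8.

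The remaining three are target CR, PR or SD with non-target lesions not all evaluated. The total is 5 + 8 + 3 = 16. With a new lesion, the table and the definitions both give PD.

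**The three remaining combinations**

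The Missing Assessments text in Appendix 3 covers absent imaging and partly measured target lesions, but not unevaluated non-target lesions. The PR definition in Appendix 4 Table 1 requires that there be no unequivocal non-target progression. If some lesions were not seen, that can be read as satisfied (none was observed) or as unproven. Appendix 4 Table 2 settles the case, but for immune-modified RECIST only. The one Appendix 3 row that names it returns NE, in a table meant for other patients.

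**The case against.** The strongest reply is that the table announces its own inapplicability. An investigator with measured target lesions, seeing a heading for patients without any, would turn to the definitions. These are in the protocol: target criteria, non-target criteria and new lesions in Appendix 3, and the RECIST v1.1 summary column in Appendix 4. On that view the eight conflicts are hypothetical. This largely stands, and it is why the practical effect is probably small. It does not rescue the citation, because the reader must disregard the table that the appendix names.

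A second reply is that Appendix 3 presents itself as selected sections of RECIST v1.1, so the published standard governs where the excerpt is silent. That has force for a gap. But the appendix also says it departs slightly from the publication, and here it is not silent: it prints a table and cites it. A site cannot tell from the text that this is not one of the departures.

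Third, the study generates hypotheses and plans no formal test (Section 6.1), and no analysis method is wrong. This is correct. The point is an internal inconsistency in the endpoint rules, not a faulty choice of analysis.

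Fourth, the enumeration assumes both lesion types. It does not cover patients with target lesions only, for whom the printed table has no row. The count of 8 in 16 describes combinations and says nothing about how many patients would be affected.

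**Conclusion.** The point holds. Appendix 3 cites the wrong table for the primary endpoint, and that table fits no patient the protocol admits. Used as cited, it conflicts with the protocol's definitions in 8 of 16 combinations, 5 of which alter a timepoint's ORR or DCR status. How often sites would use it this way is unknown. The count assumes both target and non-target lesions, no new lesion, and that Non-CR/non-PD and NE are not counted as response or disease control.

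Three stronger readings are tempting, and the documents do not support them:

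- A reader might infer that ORR is undefined. It is not, because the definitions classify most timepoints once the table is set aside.
- A reader might infer that sites have no rule at all for non-target lesions not all evaluated. The wording in Appendix 4 Table 1 can be applied to that case; it is ambiguous and not explicit in Appendix 3, which is a lesser fault.
- A reader might infer that every miscoded patient shifts a cohort's ORR or DCR. Three of the eight conflicts change neither. Table 1 gives a single-timepoint status, while ORR needs CR or PR on two consecutive assessments at least 4 weeks apart, so one miscoded timepoint need not move it.

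This should be corrected, but it does not put the analysis in doubt.

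**What to change.** Replace Appendix 3 Table 1 with the RECIST v1.1 table for patients with target lesions, with or without non-target lesions. It should have target, non-target and new-lesion columns and the outcomes CR, PR, SD, PD and NE. It should include explicit rows for target CR, PR and SD when non-target lesions are not all evaluated. Remove or renumber the non-target-only table. Confirm that the lead-in sentence and the Special Notes then point to the right table, and that the response eCRF follows it.

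The cost is one appendix table, two cross-reference checks and one eCRF check. No new data are needed.
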